8.3. Data Analysis

8.3.1. Wound Size Analysis

Descriptive statistics for initial wound size (measured at the Initial Visit) and final wound size (measured at Final Visit) will be calculated. These statistics include measures of central tendency (e.g. mean, median), variability (e.g. standard deviation). A 95% confidence interval for mean wound size change will also be calculated, assuming normality of the data. For exploratory purposes, a paired samples t-test will be conducted on wound size at the Initial Visit vs. Final Visit to identify any significant differences in wound size over the course of the study; if the data are not normally distributed, a non-parametric test will be used. Finally, change in wound size over time, using data from each visit may be modeled, using other variables such as demographic and baseline data, to better understand predictors of wound closure.

8.3.2. BWAT Analysis

Descriptive statistics for BWAT score from the Initial Visit and the Final Visit will be calculated. Measures of central tendency and variability will also be provided, and a paired samples t-test conducted on the change in BWAT score from the Initial Visit and Final Visit will be calculated for exploratory purposes; non-parametric methods will be used if the data are not normally distributed. Further exploration of the data may occur via modeling BWAT score from each visit and including other variables such as demographic and baseline data to better understand predictors of wound closure.

8.3.3. Pain Scale Analysis

Descriptive measures of central tendency and variability will be provided for pain rating at the Initial Visit and the Final Visit. A 95% confidence interval for mean change in pain will also be calculated, assuming normality of the data. For exploratory purposes, paired samples t-test will be conducted on wound size at the Initial Visit vs. Final Visit to identify any significant differences in wound size over the course of the study; if the data are not normally distributed, a non-parametric test will be used. Though these data are technically on an ordinal scale, the ten-point scale allows for the mean value to be more informative, and for the potential of conducting parametric tests. Finally, change in pain over time may also be modeled similarly to change in wound size.

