1. PROTOCOL SUMMARY

1.1. Synopsis

Title: A prospective case series evaluating a fibrillar collagen powder dressing to treat chronic, stalled lower-extremity wounds

Study Description: Chronic wounds are a source of significant morbidity and escalating healthcare costs. The wound care professional has a myriad of modern wound dressings to choose from when treating a wound, each of which has benefits and drawbacks. An understanding of how a given dressing performs in healing a particular wound is crucial in order to determine a clinical mapping of wound dressings to wound types; such a categorization would lead to more efficient clinical decision making and better patient outcomes. This case series will evaluate the ability of a fibrillar collagen powder to improve healing of chronic, stalled, lower-extremity wounds.

Objectives: Evaluate the ability of a fibrillar collagen powder dressing to treat chronic, stalled, lower-extremity wounds

Endpoints: **Primary:** Change in wound size over twelve week period
Secondary: 1) Change in Bates-Jensen Wound Assessment Tool score, 2) Change in reported pain level.

Study Population: Twenty adult patients with chronic lower-extremity wounds (i.e. below the knee) of greater than four weeks that have failed to respond to at least one advanced wound dressing treatment. Specific wound types include: pressure ulcers, diabetic ulcers, and venous leg ulcers.

Phase: Post-Market

Description of Sites/Facilities Outpatient podiatry clinics in the United States
Enrolling Participants:

Description of Study Intervention: Patients who meet the inclusion criteria will be provided with fibrillar collagen powder dressing (Puracol® Ultra Powder by Medline Industries, Inc.). The powder dressing will be used in

accordance with its label. After cleansing the wound by the clinical site staff, the powder is placed directly on the wound, and then the wound will be covered with an appropriate moisture retentive secondary dressing. Patients will visit the clinic twice a week to have the powder re-applied. Wound evaluations will take place once a week at the outpatient clinic, with the intervention lasting up to twelve weeks. Concurrent standard of care, such as compression for venous ulcers, will be provided.

Study Duration: Total time for study completion to allow accrual of all subjects, and appropriate treatment as per the protocol, will be approximately 12-18 months

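### The paired-test sentence in section 8.3.3 (pain) names wound size instead of pain, so as written pain has no paired test and wound size is tested twice

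*Combined protocol and SAP*

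**What the plan says.** The Synopsis (section 1.1) lists as a secondary endpoint "2) Change in reported pain level". Section 3 divides it into general pain and pain at dressing change.

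Section 8.3 then takes the endpoints in turn:

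- **8.3.1, wound size:** descriptive statistics, a 95% confidence interval for mean change, and for exploration "a paired samples t-test will be conducted on wound size at the Initial Visit vs. Final Visit", with a non-parametric test if normality fails.
- **8.3.2, BWAT:** descriptive statistics and "a paired samples t-test conducted on the change in BWAT score"; for the fallback, "non-parametric methods will be used if the data are not normally distributed".
- **8.3.3, pain:** descriptive statistics and a 95% confidence interval for mean change in pain under normality. The test sentence follows: "For exploratory purposes, paired samples t-test will be conducted on wound size at the Initial Visit vs. Final Visit", with the stated aim "to identify any significant differences in wound size over the course of the study" and a non-parametric fallback. The next sentence begins "Though these data are technically on an ordinal scale" and argues that the scale nevertheless allows "for the potential of conducting parametric tests". The section ends with optional modelling of pain over time.

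**The concern.** The pain section specifies a test on a different endpoint. An analyst who follows the text exactly would repeat the wound-size test of 8.3.1 and run no paired test on pain. The non-parametric fallback in that sentence would also attach to wound size.

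What is at stake is traceability. A reported p-value for pain, or a switch to a non-parametric method for pain, would not match the wording of 8.3.3, whereas the same results for BWAT would match 8.3.2. The fallback matters more for pain than the parametric test does, because the plan itself calls the pain data ordinal.

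**Working it through.** No stated figure in the plan bears on this point, so the check is mainly a comparison of texts.

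**1. The two test sentences side by side.** They were compared word by word, split on spaces.

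| | 8.3.1 (wound size) | 8.3.3 (pain) |
|---|---|---|
| Words in the sentence | 47 | 46 |
| Words shared, in the same order | 46 | 46 |
| Only difference | article *a* before *paired* | article absent |
| Variable named | wound size | wound size |

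In the 8.3.3 sentence *wound size* occurs 2 times and *pain* 0 times.

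**2. Could a second wound-size test be intended?** Section 8.3.1 already specifies that test on the same two visits, so a repeat would add nothing. The sentence after the test in 8.3.3 justifies parametric testing of ordinal data. Wound size is an area in cm² calculated by the camera software (section 6.3.2) and is not ordinal. The ordinal measure is the 0-10 verbal pain rating (section 6.3.3). The justification makes sense only if the test was meant for pain.

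**3. Paired tests by endpoint.**

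| Endpoint | As written | Noun corrected | Noun corrected, both pain ratings tested |
|---|---|---|---|
| Wound size | 2 (8.3.1, 8.3.3) | 1 | 1 |
| BWAT | 1 (8.3.2) | 1 | 1 |
| Pain | 0 | 1 (rating not specified) | 2 |
| Distinct tests | 2 | 3 | 4 |

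No other section supplies a paired test on pain.

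**4. How much the pain confidence interval already covers.** Let d be the within-patient change, with mean d̄ and standard deviation s, and take all n = 20 patients as evaluable. The t-based 95% interval is d̄ ± t(0.975; 19) × s/√20, with t(0.975; 19) = 2.093. It excludes zero exactly when |d̄|/(s/√20) > 2.093, which is the rejection rule of the two-sided 5% paired t-test. In 5000 simulated normal samples of 20 the two decisions agreed 5000 times. With fewer evaluable patients the critical value changes but the equivalence does not.

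The interval therefore already carries the 5% decision of the missing t-test. It has no substitute for the non-parametric route, because it is specified only under normality.

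**The case against.** The strongest reply is that this is an editorial slip, not a choice of analysis. The heading, the two sentences before and the sentence after all concern pain, so no reader would be misled for long. The confidence interval already gives the same 5% decision as the paired t-test. A repeated wound-size test on the same data would only repeat its result. Pain is also not simply worse served than BWAT, since 8.3.2 gives BWAT no confidence interval.

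Most of this stands, and it is why the point is minor. It does not remove the error. The operative rule for a listed secondary endpoint names the wrong variable, and the right one has to be inferred. The fallback can be read as belonging to pain only by the same inference.

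Two further objections are fair. That the sentence was carried over from 8.3.1 is itself an inference, although a 46-word match makes it a strong one; the error does not depend on it. The question of which pain rating is tested is also separate from the wrong noun: correcting the noun alone gives three distinct tests, and the fourth comes only from the added clarification.

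**Conclusion.** Section 8.3.3 is wrong as written. Its test sentence names wound size where pain is evidently meant, which leaves pain with no paired test and no non-parametric fallback and states the wound-size test twice.

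The size is minor. The test is exploratory, the 20 patients were chosen without a power analysis (section 8.1), and no primary result, sample size or type I error rate depends on the sentence. The descriptive statistics, confidence interval and optional modelling for pain are unaffected. The documents contain no pain data, so no effect on the conclusions about pain is claimed.

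The equivalence of interval and test assumes that the interval is t-based, which the plan implies by assuming normality but does not state.

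**What to change.** In the test sentence of 8.3.3, replace *wound size* with *pain rating* in both places and restore the missing article. The paired t-test, its aim and its fallback then all refer to pain. Naming the fallback, for example the Wilcoxon signed-rank test, would help but is optional, since 8.3.1 and 8.3.2 do not name theirs.

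As a separate clarification, add a clause saying that the analysis is done once for current (general) pain and once for dressing-change pain. Section 3, section 6.3.3 and the Wound Photo Case Report Form (11.3.2) already keep these apart, while 8.3.3 refers only to a pain rating.

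The cost is two replaced phrases and one clause. Data collection, visits, sample size and the primary analysis stay as they are.

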9.2. Clinical Monitoring

The Clinical Research Associate (CRA) will confirm that the rights and well-being of subjects are protected, and that the reported trial data are accurate, complete, and verifiable from source documents. Moreover, the CRA will confirm the conduct of the trial by the PI and site is in compliance with the protocol, GCP, and regulatory requirements as well as any applicable institution or IRB and federal or local processes. Monitoring will occur at minimum every two months during the study duration or more frequently if:

- The volume or quality of data is large or there is a backlog of review due to unexpected issues
- This would also include any large volume of CRFs to be reviewed
- The site compliance with the protocol or compliance with expected ICH/GCP and regulatory requirements is lacking or there are continuing unresolved compliance issues
- There are unexpected AE/SAE or subject safety concerns noted
- There are any unexpected inconsistencies with study product management
- There is a request for more frequent monitoring by the site
- Any mutually agreeable situation as determined by the sites and Medline

The frequency of routine monitoring may be increased to a longer interval after three monitoring cycles if on-site situations support this change. CRA will discuss this with Medline Associate Director or Clinical Manager and will inform the PI prior to implementation.

Monitoring activities will include subject eligibility, source data review, CRF completion verification, product accountability, site continued suitability, PI study oversight, compliance, and all general monitoring activities as outlined in FDAs Code of Federal Regulations and ICH/GCP guidelines that guide that activity.

Medline Industries Inc. may, on occasion, contract with external CROs to provide CRA services and those CRAs are authorized to act on behalf of Medline Industries, Inc.

It is expected that the site will be compliant with any institutional SOPs during the execution of the protocol and evidence of that compliance should be readily documented and verifiable by the CRA.

The CRA will generate an internal Medline Industries Inc. visit report that will be filed with the Medline Industries, Inc. trial master file and will provide the PI a detailed follow-up letter after each monitoring visit that will outline the completed monitoring activities as well as any identified areas of concern and the expected/applicable corrections needed. Medline Industries Inc., reserves the right to perform audit of the study activities – either routine or for-cause – as needed, and may also perform clinical monitoring audit as well.

9.3. Regulatory and Ethical Considerations

9.3.1. Confidentiality and Privacy

Participant confidentiality and privacy is strictly held in trust by the PI, his or her staff, and the Sponsor. This confidentiality is extended to cover testing of biological samples in addition to the clinical information relating to participants. Therefore, documentation, data, and all other information generated will be held in strict confidence. No information concerning the study or the data will be released to any unauthorized third party without prior written approval of the Sponsor. All study data and study records will be managed and stored in accordance with the site's HIPAA compliant policies on data storage and security. All electronic transmission of data will adhere to HIPAA Security Rules.

The study monitor, other authorized representatives of the Sponsor, representatives of the IRB and regulatory agencies may inspect all documents and records required to be maintained by the PI, including but not limited to, medical records (office, clinic, or hospital) and pharmacy records for the participants in this study. The clinical study site will permit access to such records.

A master list linking subject numbers to patient name and medical record number will be maintained in a secure database by the PI. The study participant's contact information will be securely stored at each clinical site for internal use during the study. At the end of the study, all records will continue to be kept in a secure location for at least a period of two years, or longer if dictated by the reviewing IRB, Institutional policies, Sponsor requirements, or ICH/GCP and FDA requirements. The PI will agree to notify Sponsor of any intent to move or destroy these documents.

Study participant research data, which is for purposes of statistical analysis and scientific reporting, will be maintained at the research sites on the CRFs. Copies of the CRFs, which will not contain any identifiable information, will be provided to the Sponsor for the purposes of data analysis. The study data entry and study management systems used by clinical sites and by Medline Industries, Inc. research staff will be secured and stored in an access controlled locked drawer (any paper forms) and password protected (electronic records). At the end of the study, all study databases that are not already de-identified will be de-identified and archived at Medline Industries, Inc.

9.3.2. Safety Oversight

Given that this is a post-market study on a device used in accordance with its labeling, there is minimal safety risk to participants. The PI is a doctor of podiatric medicine and trained in treating these types of wounds. In the event there are any AEs or SAEs, the PI will review them and make any necessary safety determinations as needed.

9.3.3. Data Handling and Record Keeping

Data collection is the responsibility of the clinical trial staff at the site under the supervision of the PI. The investigator is responsible for ensuring the accuracy, completeness, legibility, and timeliness of the data reported.

All source documents of any kind (electronic, paper, etc.) should be completed in accordance with Good Documentation Practices (GDP) to ensure accurate interpretation of data. CRFs will be created for each subject. The CRA will verify the data entered into the CRF with the site source regardless of the type of source. The site will be responsible for developing a written process that ensures the CRA is able view the source data.

Data from the CRFs will be entered into an electronic spreadsheet via dual-entry to assure no errors. Data will be transferred to and analyzed with SAS for statistical analysis. SAS allows for internal quality checks, such as automatic range checks, to identify data that appear inconsistent, incomplete, or inaccurate. Medline Industries, Inc. will be responsible for overseeing final data analysis and confirmation of results.

9.3.4. Study Records Retention

Study documents should be retained until at least two years have elapsed since the formal discontinuation of the study intervention or as required by any applicable FDA guidelines or for a longer period if required by local regulations. No records will be destroyed without the written consent of the Sponsor, if applicable. It is the responsibility of the Sponsor to inform the PI when these documents no longer need to be retained. The PI is required to notify Medline if the location of the stored documents is changed after it is defined at the time of the Close Out Visit at study end.

9.3.5. Study Discontinuation

This study may be temporarily suspended or prematurely terminated if there is sufficient reasonable cause. Written notification, documenting the reason for study suspension or termination, will be provided by the suspending or terminating party to the PI, Sponsor, and IRB. If the study is prematurely terminated or suspended, the PI will promptly inform the IRB and Sponsor and will provide the reason(s) for the termination or suspension.

Circumstances that may warrant termination or suspension include, but are not limited to:

- Determination of unexpected, significant, or unacceptable risk to participants as determined by AE review
- Insufficient compliance to protocol requirements
- Data that are not sufficiently complete and/or evaluable

The study may resume once concerns about safety, protocol compliance, and data quality are addressed, and satisfy the Sponsor and/or IRB.

9.3.6. Study Closeout

Upon completion of the study, Medline and/or its designees will notify the site of closeout related procedures and will coordinate with the site the return of equipment and/or any unused

product. Medline CRA will communicate closely with the PI at that time point and will review all close out steps and materials. All study data, related study documents, and unused study product, will be returned to the Sponsor. Sponsor will provide the facility with a summary of the activities and findings after the final analysis of the data has been completed. The site will also notify the IRB that the study has completed.

9.3.7. Conflict of Interest Policy

The independence of this study from any actual or perceived influence is critical. Therefore, any actual conflict of interest of persons who have a role in the design, conduct, analysis, publication or any aspect of this trial will be disclosed and managed.

9.4. Protocol Deviations

It is the responsibility of the PI and study staff to use continuous vigilance to identify and report deviations on a routine basis. All deviations must be addressed in study source documents, and reported to Medline Industries, Inc. Protocol deviations must be sent to the reviewing IRB per their policies. The site investigator is responsible for knowing and adhering to the reviewing IRB requirements

9.5. Abbreviations and Terms

AE	Adverse Event
BWAT	Bates-Jensen Wound Assessment Tool
CFR	Code of Federal Regulations
CRA	Clinical Research Associate
CRF	Case Report Form
DPM	Doctor of Podiatric Medicine
GCP	Good Clinical Practice
GDP	Good Documentation Practice
ICH	International Conference on Harmonization
IFU	Instructions for Use
IRB	Institutional Review Board
PI	Principal Investigator

11. APPENDIX

11.1. Products used in study

11.1.1. Investigational Product: Puracol® Ultra Powder Label and Instructions for Use

Fibrillar dressing for treating chronic, stalled wounds

MED-2018-DIV71-008

23 August 2018

V 1.0

CONFIDENTIAL

[name]
www.medline.com

Instructions For Use

PURACOL® ULTRA POWDER COLLAGEN WOUND DRESSING

[name]
www.medline.com

Description

PURACOL® ULTRA POWDER is a powder-like fibrillar collagen microsponge, a native primarily Type I porcine dermis collagen that is composed of specific amino acids. The building blocks that make up collagen are called amino acids. Collagen is primarily present in connective tissue and found in skin, tendon and ligament. PURACOL® ULTRA POWDER is a sterile wound exudate absorber and filler. PURACOL® ULTRA POWDER protects the wound bed and delicate newly regenerated granulation tissue. PURACOL® ULTRA POWDER interacts with the wound by absorbing the wound's fluids forming a gel-like barrier and provides a moist healing environment.

INDICATIONS FOR USE:

PURACOL® ULTRA POWDER is indicated for the management of full and partial thickness wounds including: pressure ulcers, diabetic ulcers caused by mixed vascular origin, venous ulcers, donor and graft sites, abrasions, traumatic wounds healing by secondary intention, dehisced surgical wounds, first and second degree burns.

WARNINGS AND PRECAUTIONS:

- For external use only.
- If redness, swelling or bleeding continues, seek the help of a medical professional.
- Do not use on individuals with a known sensitivity to collagen.
- Product is provided sterile in unopened, undamaged packaging. Do not use if the package has been opened prior to receipt or damaged in anyway.
- PURACOL® ULTRA POWDER collagen wound dressing is for single patient use, single use only. Unused product must be discarded.
- Caution: Federal (USA) Law restricts this device to sale by or on the order of a physician or properly licensed health care professional.

INSTRUCTIONS FOR USE:

- Cleanse the burn or wound in accordance with normal procedures.
- Apply, from the product envelope, a uniform layer of PURACOL® ULTRA POWDER directly into the wound site.
- Cover the wound with an appropriate moisture retentive secondary dressing.
- Reapply PURACOL® ULTRA POWDER and redress as needed.

REMOVAL INSTRUCTIONS:

PURACOL® ULTRA POWDER does not need to be removed from the wound site. Puracol® Ultra Powder is naturally broken down in the wound healing process.

CHANGE FREQUENCY:

As needed or as indicated by the amount of drainage.

STORAGE:

Store in dry conditions at room temperature (59-86°F). Extreme temperatures may denature collagen, but will not affect performance of product.

Single use only.

Sterility guaranteed in unopened, undamaged package.

This product is not made with Natural Rubber Latex.

REF

MSC8801EP

Size:

PURACOL® ULTRA POWDER, 1 gram envelope

Estimated Dressing Yield:

(for 4x4", 10cmx10cm surface area)
2"x2" surface area

DEFINITION OF SYMBOLS:

LOT - Lot number

EX - Expiration date

[name]
www.medline.com

©2017 Medline and Puracol are registered trademarks of Medline Industries, Inc. Made in the USA for Medline Industries, Inc., [name] USA.

RC17VBL

